6.2. Exclusion criteria

- Enrolled previously in the trial 3 times
- Respiratory infection or bronchiectasis exacerbation 4 weeks prior to screening and/or between screening and randomisation^c
- Antibiotic or corticosteroid 4 weeks prior to screening and/or between screening and randomisation^c
- Active allergic bronchopulmonary aspergillosis (defined by International Society for Human and Animal Mycology criteria) on steroids and/or anti-fungals
- Nontuberculous mycobacterial infection on antibiotic therapy
- Immunodeficiency on immunoglobulin replacement
- A primary diagnosis of COPD or asthma (a secondary diagnosis of COPD or asthma is permitted)
- Cystic fibrosis
- Active malignancy except non-melanoma skin cancer
- Currently taking brensocaticib
- Use of any investigational drugs within five times of the elimination half-life after the last dose or within 30 days, whichever is longer. Current enrolment in non-interventional, observational studies will be allowed
- Currently pregnant or breast-feeding
- Women of childbearing age and not practicing an acceptable method of birth control, see section 8.11

^c In the event of a respiratory infection or bronchiectasis exacerbation during the screening period, the screening period may be extended, once only by up to 8 weeks, to ensure that randomisation occurs at least 4 weeks after the last dose of antibiotics is given.

6.3. Open treatment arm specific exclusion criteria

6.3.1. Arm 2: Disulfiram

- Currently on Disulfiram (patients should have a washout period of at least 30 days from last dose if they have previously received this medication)
- Hypersensitivity to Disulfiram
- Participant, or investigator objects to randomisation to Disulfiram
- Does not agree to cease consumption of alcohol during intervention and for 14 days following treatment discontinuation
- Chronic liver disease
- Alanine transaminase (ALT)>135 U/L at screening,
- Bilirubin >30 umol/L at screening.
- Uncompensated cardiac failure
- Coronary artery disease (diagnosis of stable or unstable angina, previous myocardial infarction)
- Previous history of stroke or transient ischaemic attack
- Uncontrolled hypertension
- Hereditary problems of galactose intolerance, total lactase deficiency or glucose-galactose malabsorption
- Recent psychiatric exacerbation
- Any significant acute or chronic psychiatric condition, including severe personality disorder, psychotic disorder or suicide risk.
- Hypothyroidism
- Porphyria

- Diabetes Mellitus
- Epilepsy

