7.1.2. Screening

At the screening visit (Visit 1) the procedures as detailed in the Schedule of Procedures, Appendix 4, will be carried out.

Assessment of eligibility will be carried out by the PI or other medically qualified delegate. Eligibility will be assessed at Visit 2, randomisation/baseline once all results have been reviewed.

Details of all participants consented to the trial and screened for eligibility will be recorded on the Enrolment and Randomisation Log, this will detail if a participant fails screening or goes on to be randomised.

Where an ineligible participant's medical condition, including ineligibility due to a recent infection, or concomitant medications change sufficiently so that they are deemed potentially eligible for the trial they may be rescreened one further time. All screening procedures will be repeated, including informed consent, and eligibility checked.

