Spirometry: post bronchodilator spirometry at visits will be carried using American Thoracic Society/European Respiratory Society's guidelines. Forced Expiratory Volume (FEV1) forced vital capacity (FVC) and Forced Expiratory Flow at 25-75% (FEF25-75) will be measured.

Questionnaires: as per schedule of procedures.

Blood samples: collected, processed, and stored as per laboratory manual. Full blood count, urea and electrolytes, liver function tests will be analysed by the local NHS laboratory. Samples will also be taken for trial outcomes. Additional blood samples will be collected for future biomarker and molecular microbiology research, dependent on participant consent, see section 7.2.1. A maximum of 100 ml of blood will be obtained at any visit.

Sputum sample: a sputum sample will be collected, processed, divided and stored as per laboratory manual. Participants will be asked to bring a spontaneous early morning sputum sample with them to visits from their second visit onwards. Where a participant is unable to produce a sputum sample at a visit a hierarchical approach to obtaining sputum samples will be used:

1. spontaneous sputum sample produced at the visit
2. spontaneous early morning sputum brought from home on the day
3. spontaneous early morning sputum brought in within the following 48 hours after the scheduled visit.
4. Induced sputum at sites able to perform induced sputum according to local protocols.

A sputum sample will be analysed locally for active neutrophilic inflammation at screening/baseline using NEATstik.

A sample will also be taken for trial outcomes. Additional sputum sample will be taken for future biomarker and molecular microbiology research, see section 7.2.1.

Nasal sample: brushing of the inferior turbinate will be performed to obtain nasal epithelial cells and the brush then placed into media for storage. Participants should not have a nasal brushing performed if they are receiving anticoagulants (Oral anticoagulants or warfarin) or have a history of deviated nasal septum, base of skull fracture or severe epistaxis. If any of these are present the nasal brushing will be omitted.

Safety assessments: participants will be requested to attend an unscheduled visit if they experience a bronchiectasis exacerbation or any other safety concern.

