16.4. Appendix 4 – Schedule of Procedures

	Visit 1 Screening	Visit 2 Baseline	Visit 3	Visit 4	Visit 5	Visit 6	Safety visit
	Days -35 to 0	Day 0	Day 7	Day 14	Day 28	Day 56	If required
Informed consent	X						
Eligibility check	X	X					
Demographics	X						
Medical history	X						
Concomitant medications	X	X	X	X	X	X	X
Physical examination	X						
Height & weight	X						
Record AEs		X	X	X	X	X	X
Record exacerbations		X	X	X	X	X	X
BP, pulse, temp, O ₂ stats	X	X	X	X	X	X	X
EKG	X						
6 minute walk test		X			X		
Post bronchodilation spirometry	X	X	X	X	X	X	X
QoL-B	X	X	X	X	X	X	
BIM baseline		X					
BIM follow-up			X	X	X	X	
BEST diary		X	X	X	X		
Full blood count, urea and electrolytes, liver function tests	X			X	X	X	X
Research blood sample for endpoint analyses		X	X	X	X	X	
Sputum sample for screening eligibility (NEATstik) ^a	X						
Research sputum sample for endpoint analyses		X	X	X	X	X	
Nasal sample		X			X		
Pregnancy test, if required	X	X	X	X	X		
Randomisation		X					
Dispensing of trial drugs		X					
Drug accountability					X		
Sub-study only							
Pulse wave velocity (PWV)		X			X	X	
Full-field Laser perfusion imaging (FLPI)		X			X	X	
Waist & Hip measurement		X					

^a If NEATSTIK is not available for screening, a frozen sputum sample will be shipped to the central laboratory in Dundee where the immunoassay will be performed and used to confirm eligibility.

Missed trial assessments or trial medication, or visits completed outside the visit window, will not be reported as breaches, where this is due to participant choice or a clinical decision.

Visits should be every as per schedule wherever possible. If a participant is unable to attend on the day of visit a delay of up to 2 days is accepted.

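### When screening is extended after an infection, disulfiram's ALT and bilirubin limits can rest on a liver panel more than 35 days old, because no repeat before randomisation is required (minor; cheap to fix)

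*Protocol*

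**What the plan says.** Section 6.3.1 sets two numerical liver exclusions for Arm 2: "Alanine transaminase (ALT)>135 U/L at screening" and "Bilirubin >30 umol/L at screening". Chronic liver disease is a separate exclusion, and so is an objection to disulfiram by the participant or the investigator.

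In Appendix 4 the row "Full blood count, urea and electrolytes, liver function tests" is marked at Visit 1 (days -35 to 0), at days 14, 28 and 56, and in the safety visit column. It is not marked at Visit 2 (day 0), where randomisation and dispensing both occur. Section 7.1.2 places the eligibility decision there: "Eligibility will be assessed at Visit 2, randomisation/baseline once all results have been reviewed".

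Footnote c to 6.2 says that after a respiratory infection or exacerbation during screening "the screening period may be extended, once only by up to 8 weeks", so that "randomisation occurs at least 4 weeks after the last dose of antibiotics is given". It names no test to be repeated. The separate rescreening route in 7.1.2 does: "All screening procedures will be repeated, including informed consent, and eligibility checked".

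Section 7.7 adds that "participants will be requested to attend an unscheduled visit if they experience a bronchiectasis exacerbation or any other safety concern".

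**The concern.** The two numerical limits are what would catch a new liver abnormality; the chronic liver disease exclusion would not. They carry some weight, because the Rationale supports 400 mg daily, twice the SmPC maximum of 200 mg although within the 500 mg it cites from the British National Formulary and practice, partly by pointing to the exclusion of people with liver disease. Appendix 1 describes hepatotoxicity ranging up to rare fulminant failure, and says that it also occurs without previous alcohol misuse.

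The extension route is where the Visit 1 result is oldest. It is also where the participant has just had an illness and probably an antibiotic course. Someone whose ALT or bilirubin rose above the limit after Visit 1, with nobody measuring it, still satisfies 6.3.1 on its natural reading. That person could start disulfiram and have no scheduled liver test until day 14 of a 28-day course.

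**Working it through.** The protocol states no figure for the age of the liver result, so there is nothing to reproduce. The check is day arithmetic on its windows.

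**Inputs from the protocol.** Screening window: 35 days (Appendix 4). Extension: once, up to 8 weeks = 8 × 7 = 56 days (6.2, footnote c). Interval after the last antibiotic dose: at least 4 weeks = 28 days (same footnote). First scheduled liver test on drug: day 14 (Appendix 4).

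**Assumptions, not in the protocol.** Infection starts *s* days after Visit 1, antibiotics start the same day, and the course lasts *c* days. For illustration, *s* = 14 and *c* = 7 to 14.

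**Age of the Visit 1 result at randomisation**
- No extension: at most 35 days.
- Permitted maximum with the extension: 35 + 56 = 91 days. Cases that depend on the extension therefore span 36 to 91 days.
- Earliest permitted randomisation after an antibiotic-treated infection: age = *s* + *c* + 28.
  - *s* = 14, *c* = 7: 14 + 7 + 28 = 49 days.
  - *s* = 14, *c* = 14: 14 + 14 + 28 = 56 days.
  - *s* = 35, *c* = 14: 35 + 14 + 28 = 77 days.
- The age exceeds 35 days whenever *s* + *c* > 7. With a course of 7 days or more, any infection starting from the day after Visit 1 has this effect.

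So 91 days is reached only when randomisation also falls later than the earliest date allowed; the illustrative 49 to 56 days is 14 to 21 days beyond the ordinary maximum.

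**Interval between the qualifying result and the first scheduled on-drug test**
- No extension: at most 35 + 14 = 49 days.
- Illustration: 49 + 14 = 63 to 56 + 14 = 70 days.
- Extreme: 91 + 14 = 105 days.

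**Age at randomisation of a panel taken at an exacerbation safety visit**
- Taken on or before the last antibiotic dose: at least 28 days.
- Taken when the assumed course starts: at least 28 + 7 = 35 to 28 + 14 = 42 days.

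**Wording compared.** Section 6.1 has NEATstik positivity judged at screening or baseline, 6.2 runs the infection and antibiotic exclusions from screening through to randomisation, and Appendix 4 repeats the pregnancy test at Visit 2. The liver limits refer to screening alone.

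**The case against.** The best defence is that safeguards already exist.

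- **The safety visit.** The liver row is marked in the safety visit column of Appendix 4, where the words *if required* describe the visit and not the test. Section 7.7 asks participants with an exacerbation to attend such a visit. This stands as a partial safeguard: many of those concerned may have a second panel. But attendance is only requested, 7.7 names exacerbations and safety concerns while footnote c also covers other respiratory infections, and a panel taken by the last antibiotic dose is at least 28 days old at randomisation.
- **Investigator objection.** Section 6.3.1 lets the investigator object to disulfiram, and a medically qualified person reviews all results at Visit 2. A reader might infer that the protocol allows disulfiram to start despite a known raised ALT. It does not oblige anyone to do that, and the objection clause gives a direct way to prevent it. What remains is the rise that nobody measured, which no review of existing results can reveal.
- **Meaning of *at screening*.** It could be read as the whole extended period, so that a later panel counts. That reading is possible, since 6.1 separates the screening visit from the screening period. Even so, no later panel is required, and nothing says which of two results governs.
- **Size.** The 91 and 105 days stack maxima, and the documents do not show how many of the 42 disulfiram participants would have an extension or newly exceed a limit. An antibiotic-related rise would also have to persist through the 28-day interval to matter at the first dose. This objection stands and is why the point is minor.

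**Conclusion.** The point holds as a minor, cheaply corrected gap. On the extension route, the ALT and bilirubin limits can be met with a result more than 35 days old that predates an infection and its antibiotics, and no newer panel is required before the first dose. The age is 49 to 56 days under the assumed onset day and course length, and 91 days at the permitted extreme. If the 8 weeks were read as the total length of screening, the ceiling would be 56 days, still above 35. The conclusion rests on the text of 6.2, 6.3.1, 7.1.2, 7.7 and Appendix 4; the number of people affected is unknown. Ordinary screening and rescreening are not affected, and neither is the power or type I error of the trial.

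A reader might go further and infer that on-treatment liver safety is uncontrolled, because no ALT or bilirubin level for stopping disulfiram is given. The documents do not support that. There is a panel at day 14, safety visits include one, 7.10 lets the investigator withdraw a participant, 9.2 has medically significant laboratory findings reported as adverse events, and under 10.4 the DMC reviews safety after the tenth participant in each arm reaches day 28. Leaving the decision to stop to clinical judgement within that framework is not counted as a fault here.

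**What to change.** Two short changes.

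1. In 6.3.1, state that both the ALT and the bilirubin limit apply to the latest result available before randomisation.
2. In footnote c to 6.2, require a local liver panel, reported before randomisation, for every participant whose screening is extended and who is otherwise eligible for Arm 2. Say that it is drawn after the intercurrent episode; otherwise a panel from the exacerbation visit, already 28 or more days old, would satisfy the rule.

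The cost is one routine blood test in that subgroup. Because randomisation and dispensing share Visit 2, the sample must be drawn early enough for the local laboratory to report first. That may mean an extra attendance, at the £100 per visit in 7.1.4. A few participants may become ineligible for Arm 2 only; under 7.3 they can still be randomised among the other open arms for which they qualify. The target of 42 per arm and the scheduled follow-up visits do not change.

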6.3.2. Arm 3: Dipyridamole

- Currently on Dipyridamole (patients should have a washout period of at least 30 days from last dose if they have previously received this medication)
- Hypersensitivity to Dipyridamole
- Participant, or investigator, objects to randomisation to Dipyridamole
- Currently on dual antithrombotic therapy (aspirin or P2Y12 inhibitor plus anticoagulation)
- Current on direct oral anticoagulants (Dabigatran, Rivaroxaban, Edoxaban, Apixaban, Betrixaban or drugs in the same class) or long-term warfarin
- Any major trauma or haemorrhage including gastrointestinal bleeding, operation within the past 30 days
- Coagulation disorder
- Severe coronary artery disease (unstable angina, recent myocardial infarct in 30 days, decompensated/unstable severe left systolic dysfunction, uncontrolled heart failure)
- Myasthenia gravis

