2.1. Assessment and Management of Risk

This trial is categorised as: Type B = Somewhat higher than the risk of standard medical care

The trial treatments are all repurposed drugs already approved for use in conditions other than bronchiectasis.

Arm 1: Usual care

Arm 2: Disulfiram

Disulfiram is an alcohol deterrent compound licensed for use as an adjuvant in the treatment of drinking problems. The most common adverse reaction (AR) reported during treatment is alcohol reaction. Disulfiram–ethanol reactions often develop within 15 minutes after exposure to ethanol; symptoms usually peak within 30 minutes to 1 hour, and then gradually subside over the next few hours. Symptoms may be severe and life-threatening. Participants will be informed of the reaction risk and must agree to abstain from alcohol during treatment and for up to 14 days after discontinuation.

Arm 3: Dipyridamole

Dipyridamole is licensed for use in secondary prevention of ischaemic stroke and transient ischaemic attacks and as an adjunct to oral anti-coagulation for prophylaxis of thromboembolism associated with prosthetic heart valves. The most commonly reported adverse effects are headache, dizziness, diarrhoea, nausea (very common, $\geq 1/10$) and angina pectoris, vomiting, rash, myalgia (common, $\geq 1/100 < 1/10$).

Arm 4: Doxycycline

Doxycycline is licensed for use in the treatment of a variety of infections caused by susceptible strains of Gram-positive and Gram-negative bacteria and certain other micro-organisms. The most common adverse effects observed in patients receiving tetracyclines, including doxycycline, are hypersensitivity, headache, nausea/vomiting, photosensitivity reaction rash including maculopapular and erythematous rashes (common, $\geq 1/100 < 1/10$).

Management of risk is described in Appendix 1. However, this is the first use of these medications in this patient population, hence there is the *possibility* of additional unknown risks.

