8.9. Known drug reactions and interaction with other therapies, open treatment arms

Treatment	Known drug reactions	Known drug interactions
-----------	----------------------	-------------------------

Arm 2: Disulfiram
	
Disulfiram-alcohol reaction
	
Alcohol - Disulfiram has several CYP450 enzyme interactions, which results in the interference of the metabolism of various drugs. Disulfiram inhibits CYP2E1 CYP1A2, and is activated by CYP3A4. Amitriptyline – increased disulfiram alcohol reaction Chlorpromazine – increased disulfiram alcohol reaction Benzodiazepines – enhanced sedative effect Phenytoin – increased phenytoin concentration and needs dose adjustment Warfarin – increased anticoagulant effect and needs dose adjustment Rifampicin – increased concentration due to reduced metabolism and renal excretion Metronidazole, Isoniazid and Paraldehyde were anecdotally found to increased risk of psychotic reaction

Arm 3: Dipyridamole
	
Very common, $\geq 1/10$ Headache Dizziness Diarrhoea Nausea
 
Common, $\geq 1/100$ to $< 1/10$ Rash Angina pectoris Vomiting Myalgia
 
Unknown drug reactions are detailed in the RSI.
	
Adenosine - Dipyridamole inhibits the uptake and degradation of adenosine in the blood vessels and cells. Adenosine use should be adjusted or avoided. Antiplatelets and anticoagulation – increases bleeding risk. Antihypertensives – increases risk of hypotension. Alcohol – increase the risk of hypotension. Cholinesterase Inhibitors in Myasthenia Gravis – worsens symptoms

Arm 4: Doxycycline
	
Common, $\geq 1/100$ to $< 1/10$ Hypersensitivity Headache Nausea/vomiting Photosensitivity reaction, rash including maculopapular and erythematous rashes
 
Uncommon, $\geq 1/1000$ to $< 1/100$ Vaginal infection Dyspepsia
 
Rare and unknown drug reactions are detailed in the RSI.
	
Antacids – may impair absorption of doxycycline Barbiturates, Carbamazepine, phenytoin, and primidone – may reduce exposure to doxycycline Warfarin - increased anticoagulant effect and needs dose adjustment. Oral contraception – few cases of breakthrough bleeding or pregnancy Alcohol – reduced doxycycline half-life Retinoids – increased risk of benign intracranial pressure Rifampicin - may reduce exposure to doxycycline

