8.11. Trial restrictions

	Treatment	Trial restrictions
All arms		To avoid contamination between the arms, participants who develop an exacerbation during the study and require antibiotic treatment should receive an antibiotic other than doxycycline. If participants are not able to safely avoid doxycycline during the trial period they should not be enrolled in the study.
Arm 2	Disulfiram	Alcohol Participants will be required to consent to not consuming alcohol for duration of treatment and at least 14 days after stopping treatment. Written advice will be provided to participants about how to avoid products containing alcohol during the trial period.
Arm 3	Dipyridamole	Participants should not commence new oral anticoagulant drugs during the trial period. Participants needing to initiate anticoagulants should withdraw from the study.
Arm 4:	Doxycycline	No restrictions. Exacerbations of bronchiectasis should be treated with an alternative antibiotic.
All	Nasal brushing	Participants should not have a nasal brushing performed if they are receiving anticoagulants (oral anticoagulants or warfarin) or have a history of deviated nasal septum, base of skull fracture or severe epistaxis. If any of these are present the nasal brushing will be omitted. This will not affect their participation in the trial.

WOCBP must be willing to have pregnancy testing prior to trial entry and at each research visit, unless the participant has been randomised to usual care.

A woman is considered of childbearing potential, i.e. fertile, following menarche and until becoming post-menopausal unless permanently sterile. A post-menopausal state is defined as no menses for 12 months without an alternative medical cause (including use of hormone replacement therapy).

In addition, WOCBP must be willing to use a form of a medically approved birth control method throughout the trial (and for minimum of 4 weeks after last dose), unless randomised to usual care, which include:

- combined (estrogen and progestogen containing) hormonal contraception associated with inhibition of ovulation:
 - oral
 - intravaginal
 - transdermal
- progestogen-only hormonal contraception associated with inhibition of ovulation:
 - oral
 - injectable
 - implantable
- intrauterine device (IUD)
- intrauterine hormone-releasing system (IUS)

- bilateral tubal occlusion
- vasectomised partner

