13.5. Protocol compliance

Prospective, planned deviations or waivers to the protocol are not allowed, e.g., it is not acceptable to enrol a participant if they do not meet the eligibility criteria or restrictions specified in the trial protocol. Trial staff will not implement deviations to the protocol except where necessary to eliminate an immediate hazard to trial participants.

Accidental protocol breaches can happen at any time. They will be adequately documented on the relevant forms and reported to the CI and Sponsor using the TASC Breach Reporting Form. If there is a breach of the protocol, the nature of and reasons for the breach will be documented in the trial Breach Log. Breaches from the protocol which are found to frequently recur are not acceptable, will require immediate action and could potentially be classified as a serious breach.

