Headache	
Headaches are a well-known transient side effects of dipyridamole, due to its vasodilatory properties. This often leads to discontinuation, as seen in 8% of patients who were enrolled into the dipyridamole arm in the Second European Stroke Prevention (ESPS2) Trial.
 
A bioequivalence trial comparing two different formulations of dipyridamole involving mostly young healthy adults found that 72% of volunteers reported at least one episode of headache over the course of two weeks. This bioequivalence trial also found that the volunteers are more likely to experience headache in the first week, 2-3 hours after the morning dose, and all volunteers recovered fully from the headaches regardless of severity. (Theis, Deichsel, and Marshall 1999)
	- Participants should be informed that they may experience transient headaches while initiating dipyridamole, and reassurance that it will improve with time.
Bleeding	
As an antiplatelet, patients may be at a higher risk of bleeding complications. Adding dipyridamole to anticoagulation increases the risk of bleeding by about 50% (Massel and Little 2013).
 
However, for patients not on anticoagulation, this risk was not seen in the large clinical trials performed in patients who had a Stroke or Transient Ischaemic Attack (TIA). In
	
- Participants who are on dual antiplatelet, any anticoagulant, or any coagulopathy should not be randomised to dipyridamole. Participants who are already on Aspirin are safe to be recruited.
 
- Participants who recently had any gastrointestinal bleeding, head trauma, or major operation within 30 days should not be randomised to dipyridamole

	ESPS2, patients who were randomised to placebo (n=1649) and dipyridamole alone (n=1654) reported similar events for bleeding any site, 74 and 77 respectively. ESPS2 also found that the bleeding risk between Aspirin (n=1649) and Aspirin plus Dipyridamole (n=1650) are similar at 135 and 144 events respectively (Diener et al. 1996).	

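### Section 6.3.2 does not exclude patients on two antiplatelets without an anticoagulant from dipyridamole, although Appendix 1 says they should not be randomised to it

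*Protocol*

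**What the plan says.** Section 6.3.2 of the protocol gives the exclusions specific to the dipyridamole arm. Two bullets concern antithrombotic drugs. The first is "Currently on dual antithrombotic therapy (aspirin or P2Y12 inhibitor plus anticoagulation", where the parenthesis defines the term. The second excludes patients on direct oral anticoagulants or long-term warfarin.

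Appendix 1 covers the same hazard in its dipyridamole bleeding row. The mitigation column states "Participants who are on dual antiplatelet, any anticoagulant, or any coagulopathy should not be randomised to dipyridamole", and then "Participants who are already on Aspirin are safe to be recruited". Section 2.1 sends the reader there: "Management of risk is described in Appendix 1".

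Two other places touch on the subject. The interaction table in section 8.9 notes "Antiplatelets and anticoagulation – increases bleeding risk". The arm 3 entry in section 8.11 says "Participants should not commence new oral anticoagulant drugs during the trial period".

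**The concern.** The two sections draw the line in different places. Appendix 1 separates one antiplatelet (aspirin, admitted) from two (barred). Section 6.3.2 separates patients with an anticoagulant from those without, and says nothing about two antiplatelets.

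Sites normally screen from the eligibility section, and section 13.5 makes it binding: "it is not acceptable to enrol a participant if they do not meet the eligibility criteria or restrictions specified in the trial protocol". A site could apply section 6.3.2 exactly, commit no breach of that section, and still give dipyridamole for 28 days to a patient whom the risk assessment says should not receive it. What is at stake is bleeding safety and consistent eligibility across 10 centres, not the efficacy analysis.

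**Working it through.** No power or sample-size figure is involved, so the main check is a comparison of the texts by drug category.

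| Patient's current drugs | Section 6.3.2 | Appendix 1, bleeding row | Agree? |
|---|---|---|---|
| Aspirin alone | Allowed | Allowed | Yes |
| Direct oral anticoagulant or long-term warfarin | Excluded | Excluded | Yes |
| Antiplatelet (aspirin or P2Y12 inhibitor) plus anticoagulant | Excluded | Excluded | Yes |
| Aspirin plus P2Y12 inhibitor, no anticoagulant | Not excluded | Should not be randomised | **No** |
| Other anticoagulant alone (neither a direct oral agent nor long-term warfarin) | Not named | Should not be randomised | **No** (secondary) |

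**Does another rule close the gap in the fourth row?**

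- Section 6.2 (general exclusions) does not mention antiplatelets.
- The cardiac bullet in section 6.3.2 removes unstable angina, infarction within 30 days and decompensated or uncontrolled heart failure. A stable patient more than 30 days after an infarct passes.
- Section 8.11 restricts starting oral anticoagulants. It does not cover antiplatelets already being taken.
- Section 8.9 warns of the interaction but excludes nobody.

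**Allocation.** Section 7.3 randomises equally among the open arms for which the participant is eligible. Section 6.3.1 bars patients with angina, previous infarction, stroke or transient ischaemic attack from disulfiram. Such a patient, if eligible for doxycycline, has three possible arms (usual care, dipyridamole, doxycycline) instead of four. The chance of dipyridamole is then about 1/3 rather than 1/4.

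**Evidence in the protocol.** Appendix 1 cites a large stroke-prevention trial: "bleeding risk between Aspirin (n=1649) and Aspirin plus Dipyridamole (n=1650) are similar at 135 and 144 events respectively". Treating each event as one patient (an assumption, since the text gives events):

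- Aspirin: 135/1649 = 0.0819.
- Aspirin plus dipyridamole: 144/1650 = 0.0873.
- Difference: 0.0873 − 0.0819 = 0.0054.
- Standard error: √(0.0819 × 0.9181/1649 + 0.0873 × 0.9127/1650) = 0.0097.
- 95% confidence interval: 0.0054 ± 1.96 × 0.0097, i.e. −1.4 to +2.4 percentage points.

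These counts support admitting patients on aspirin alone. They say nothing about dipyridamole added to two antiplatelets, and the protocol gives no other data on that combination.

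**The case against.** The strongest reply is that Appendix 1 is part of the protocol. Its sentence is a direct instruction, section 2.1 points to it, and section 13.5 binds sites to restrictions in the protocol as well as to eligibility criteria. On that reading the patients are already barred, and the fault is only that the rule was not carried into the checklist. This is fair as far as it goes: the omission lies in section 6.3.2, not in every part of the protocol. But sites then face two rules that disagree, and the one they screen from is the more permissive.

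Safeguards also exist. A medically qualified person assesses eligibility (section 7.1.2), concomitant drugs are reviewed at screening and baseline, the investigator may object to dipyridamole, and the DMC reviews each treatment arm after its 10th participant reaches day 28 (section 10.4). These reduce the likely harm. However, the objection is discretionary and the DMC review comes after exposure.

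The intended line is an inference. The appendix might have used dual antiplatelet loosely for dual antithrombotic. Against that, the appendix names anticoagulants separately in the same sentence and goes on to clear aspirin. In addition, the dual bullet in section 6.3.2 adds little to the anticoagulant bullet that follows it, beyond an antiplatelet combined with some anticoagulant not named there.

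Two further points stand. The aspirin comparison is context and does not measure the risk in the affected group. The same Appendix 1 sentence bars any anticoagulant, which is wider than the agents section 6.3.2 names, so one amendment should align both.

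**Conclusion.** The concern holds: section 6.3.2 is wrong as written when set against the protocol's own risk assessment, and should be corrected. The mismatch is certain from the text and needs no outside information. Its scale is unknown, because the protocol does not give the share of candidates on two antiplatelets; with the safeguards above it is probably modest. The view that section 6.3.2 should yield to Appendix 1 rests on reading the bleeding row at face value. Sample size, power and the primary analysis are unaffected.

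A minor wording point sits nearby. The hypotension row of Appendix 1 would admit a stable patient with a recent infarct, while section 6.3.2 bars any infarct within 30 days. There section 6.3.2 is the stricter, operative text, so the point is editorial.

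**What to change.** - Add an exclusion to section 6.3.2: *Currently on dual antiplatelet therapy (e.g. aspirin plus a P2Y12 inhibitor)*. Keep aspirin alone permitted, as Appendix 1 states.
- In the same amendment, make the anticoagulant bullet and Appendix 1 agree on whether every anticoagulant is excluded or only the named ones.
- Put the dual-antiplatelet item on the eCRF form that records eligibility for each arm.
- If recruitment to arm 3 has begun, check the concomitant-medication records of participants already allocated to it.
- Reword the hypotension row of Appendix 1 so that it does not admit an infarct within 30 days.

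The cost is one amendment with a few lines of text and one eCRF item. Slightly fewer participants will be eligible for dipyridamole. Those affected can still be randomised to usual care and to any other open arm whose criteria they meet.
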